Data Management and Reduction: All paper-based assessments (other than laboratory reports) will be entered into REDCap, a secure, web-based application designed exclusively to support data capture for research studies. REDCap provides an intuitive interface for data entry (with data validation), audit trails for tracking data manipulation, and automated export procedures for data downloading to statistical packages such as SPSS and SAS. Quarterly database management and data integrity audits will be conducted.

C.2.d. Statistical Considerations

C.2.d.1. **Statistics and Data Analysis** (complete data analytic plan is provided in Biostatistics Resource Core)

Aim 1: Examine the impact of exogenous progesterone on stress cue reactivity and cannabis craving and withdrawal symptoms during a period of cannabis abstinence in the natural environment.

The primary measures of interest are stress and craving ratings in response to stress-related cues using Cue Reactivity Ecological Momentary Assessment (CREMA) in heavy cannabis using women and men. Hypothesis 1: Compared to placebo, progesterone will attenuate reactivity to stress cues presented in the natural environment among women vs. men with CUD. Hypothesis 2: Compared to placebo, progesterone will attenuate cannabis craving and withdrawal symptoms among women vs. men with CUD. To assess these hypotheses multilevel generalized linear mixed effects models with repeated measures (GLMMs) will be developed using CREMA session response data from the 1-week period during active medication administration. Pre-cue stress and craving rating will be centered and used as a time varying covariate in all analysis. Least squares means and associated standard errors will be used for post-hoc comparisons of cue response and CWS scores between treatment group assignments globally as well as time-specific (AM, PM) treatment group differences. Least squares means and associated standard errors will also be used for post-hoc comparisons of craving and stress response between women and men over time. Relevant interactions will be assessed in the models.

Aim 2: Examine the impact of exogenous progesterone on stress cue reactivity during a laboratory stressor task.

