Following the initial 7-day active exogenous progesterone treatment period, participants will return for a laboratory-based stressor a session. The primary study outcomes of interest in Aim 2 are the differential craving, stress and anxiety responses of progesterone- vs. placebo-treated participants in response to the psychosocial stressor (TSST). Hypothesis 1: Compared to placebo, progesterone will attenuate stress cue reactivity during a human laboratory stress paradigm among women but not men with CUD. Immediately prior to and following the TSST (baseline, +0, +5, +30, and +60 minutes), self-reported measures of stress and craving will be collected. To assess the effect of exogenous progesterone administration on stress and craving response to the TSST, linear mixed effects models will be developed to assess differential treatment responses over time. The primary independent variable of interest will be randomized treatment assignment (progesterone vs. placebo). In addition to overall treatment differences, least squares means and associated standard errors will be used for post-hoc

comparisons between treatment groups at each post-cue time point. Additionally, sex will be added to the model and differential effect of progesterone will be assessed using an interaction term. When significant, stratified treatment effects will be compared and presented across females and males.

Aim 3: Evaluate stress, sex, and endogenous progesterone influences on cannabis craving and use.

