C.2.d.3. Power and Sample Size (complete sample size estimation is provided in Biostatistics Resource Core). In the proposed study, cue response and withdrawal data will be tested using GLMMs (assuming a Gaussian distribution) and the study will be powered to sufficiently address the smallest effect sizes determined to be clinically meaningful for the study hypothesis. Fox and colleagues (2013) examined exogenous progesterone and placebo administration on cue response in 42 cocaine dependent participants. Results indicated that female participants receiving placebo experienced larger negative emotion scores in response to stress-related cues than male participants on placebo ($\Delta=4.7$; $SD_P=3.4$; between sex Cohen's $d > 1.0$, $p < 0.01$). Fox and colleagues also found that administration of exogenous progesterone reduced stress-cue related negative emotions significantly in women ($\Delta=2.4$; $SD_P=3.4$, $d=0.71$) but not in men ($\Delta=-0.7$; $SD_P=3.3$ $d=-0.2$; treatment x sex interaction $\Delta=3.1$; $SD_P=4.7$, $d=0.67$). Assuming a similar response profile between treatment assignments and sex as above, a sample size of 64 participants (32 women, 32 men to each treatment assignment) randomized to the progesterone vs. placebo groups would guarantee 80% power with a type 1 error rate of 5% to detect the least effect size of $d=0.67$ in the stress reduction treatment x sex interaction (total $n=128$) during the 7-day, active treatment CREMA assessment period. Although the proposed study is of relatively short duration, we do anticipate 10% attrition between randomization and the end of the 1-week active treatment period and laboratory session. Thus, inflating the necessary sample size to 70 participants (35 men and 35 women), a total of $n=140$ randomized participants will be needed. Due to app issues at the beginning of the study, some initial data is unusable, so we will randomize 90 men. Additionally, data from our recently completed SCOR project, which examined daily salivary progesterone levels and cigarette smoking behavior for 14 consecutive days in untreated female participants, indicated that increased levels of daily progesterone within participant was associated with decreased cigarettes smoked per day ($\beta=-0.32$; $SE=0.14$; $p < 0.05$). To detect a similar correlation ($\beta=\pm 0.32$; $SD=1.0$) between daily progesterone levels and associated daily use metrics in the proposed study, the randomized sample of 70 women (62 with available follow up data), with 14 days of follow up use data, and with an autocorrelation of 0.9, would provide 80% power. The proposed sample size of **n=160** randomized

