
participants would provide 80% power or better to detect the proposed between sex and treatment comparisons noted in the primary study aims.

C.2.e. Design Considerations. **i) Choice of between vs. within participant design.** We considered implementation of a within-subject crossover design but opted instead for a between-subjects parallel-group comparison study for multiple reasons. Most notably, a within-subjects approach risks potential carryover effects between conditions, as well as potential dampening of cue reactivity and participant response fatigue over extended periods of testing across conditions. Additionally, withdrawal symptoms may not present consistently or reliably across multiple conditions in series without a lengthy/sustained return to *ad libitum* cannabis use between conditions. **ii) Choice of administration of progesterone during cannabis withdrawal.** Cannabis withdrawal is characterized by increased anxiety, irritability, craving, and physiological symptoms, which peak within the first 2-3 days of abstinence (Budhey et al., 2008). Acute cannabis withdrawal is therefore an ideal period to investigate potential therapeutic effects of progesterone on stress cue reactivity and craving. **iii) Focus on progesterone.** The proposed study focuses on progesterone because evidence suggests that estradiol may enhance drug reinforcement and cue-reactivity. In preclinical studies, estradiol has been shown to increase dopamine release in the ventral striatum in response to nicotine administration (Thompson et al., 1994), and facilitate methamphetamine-induced conditioned place preference (Chen et al., 2003) and cocaine self-administration (Lynch, 2008; Lynch et al., 2001). Clinical research on menstrual cycle phase has demonstrated greater smoking cue-elicited neural activity and craving response during the follicular phase (where estradiol dominates) compared to the luteal phase (Franklin et al., 2015; Mendrek et al., 2014). Likewise, women with a higher estradiol to progesterone ratio took more cigarette puffs and smoked more of a cigarette in a smoking topography study (Schiller et al., 2012). Furthermore, compared to men, women smokers in the follicular phase showed increased stress response and arousal while women in the luteal phase showed increased craving ([name] et al., 2015b). Together, evidence suggests that estradiol enhances drug reinforcement and cue-reactivity, and hence may contribute to the more deleterious outcomes observed in substance using women. Accordingly, we have focused this project on expanding knowledge about the treatment potential of progesterone (as characterized in the Significance above) by examining its effects on stress reactivity and substance use in persons with CUD. **iv) Male comparison group.** Apart from the obvious relevance of a male comparison group in studies of sex differences, there are empirical grounds for including men in proposed study. Sofuo glu et al., (2004) found that 2 oral doses of 200 mg progesterone significantly dampened cardiovascular responsiveness (diastolic BP) to iv cocaine in male, not female, cocaine users. Likewise, Fox et al., (2014) reported that exogenous progesterone vs. placebo attenuated cue-induced cocaine craving and cortisol responses in both men and women, suggesting that progesterone may also have some treatment potential for male cocaine users. Based on these and similar findings (Childs et al., 2010), we believe the proposed study's inclusion of both women and men with CUD will optimize our ability to identify therapeutic effects of progesterone that are either unique to one sex, or present in both.

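### The power claim of 80% or better covers craving and withdrawal comparisons, but the document sizes only the stress treatment-by-sex interaction, and that falls at or slightly below 80%.

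*Combined protocol and SAP*

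**What the plan says.** C.2.d.1, Aim 1, makes craving a primary rating next to stress: "The primary measures of interest are stress and craving ratings in response to stress-related cues". Hypothesis 2 of that aim is that "progesterone will attenuate cannabis craving and withdrawal symptoms among women vs. men with CUD". Aim 2 does the same for the laboratory session: "The primary study outcomes of interest in Aim 2 are the differential craving, stress and anxiety responses".

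C.2.d.3 takes its treatment effects from a study of 42 cocaine-dependent participants, and they are for negative emotion after stress cues: 2.4 in women (SD 3.4, d=0.71), -0.7 in men (SD 3.3, d=-0.2), interaction 3.1 (SD 4.7, d=0.67). With 32 per sex per arm (128 in total) it states 80% power at 5% for d=0.67 "in the stress reduction treatment x sex interaction". It then allows 10% attrition (140) and raises the men from 70 to 90 because some early data are unusable (160). The only other calculation, for daily progesterone and use in women, belongs to Aim 3. The section closes with the general statement that 160 "participants would provide 80% power or better to detect the proposed between sex and treatment comparisons noted in the primary study aims".

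C.2.e(iv), on why men are enrolled, cites a study in which "exogenous progesterone vs. placebo attenuated cue-induced cocaine craving and cortisol responses in both men and women".

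**The concern.** The conclusion is wider than its basis. One interaction on one outcome was sized, and the 80% is then stated for every sex and treatment comparison in the primary aims. The stress interaction is large partly because men moved the other way, and the document gives no reason to expect the same for craving. Its own case for enrolling men cites a craving reduction in both sexes.

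At stake is how a null result on Hypothesis 2 would be read. The hypothesis is worded as women versus men. If men share part of the benefit, the interaction test may well miss a real difference, and the general power statement would let that null pass as adequately powered. The 80% also needs checking for the stress outcome itself.

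**Working it through.** **Inputs.** From C.2.d.3: differences 2.4 (women) and -0.7 (men), SDs 3.4 and 3.3, d=0.67, 32 per cell, 10% attrition, 70 women, and 70 men raised to 90. Assumed: 1:1 allocation within sex and a two-sided 5% test (sidedness is not stated).

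**1. The plan's own figure.** The interaction is 2.4 - (-0.7) = 3.1, and men supply 0.7/3.1 = 23% of it. The SD of 4.7 is close to sqrt(3.4² + 3.3²) = 4.74, so d is the interaction over that SD, with SE sqrt(1/nw + 1/nm) for nw women and nm men per arm. At 32 per cell, SE = sqrt(2/32) = 0.25 and 0.67/0.25 = 2.68. Power = Φ(2.68 - 1.96) = 76.4%, or 75.8% by noncentral t. The stated 80% is not reproduced; it needs 35 analysable per cell at d=0.67.

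**2. Analysable numbers per arm.** Women: 70 × 0.9 / 2 = 31.5. Men: 90 × 0.9 / 2 = 40.5 if every added man has usable data, or 70 × 0.9 / 2 = 31.5 if the 20 extra only replace lost data.

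**3. Stress interaction at those numbers.** From the stated differences and SDs, SE = sqrt(2×3.4²/nw + 2×3.3²/nm).
- 31.5/31.5: SE 1.194, 3.1/1.194 = 2.60, power 73% (noncentral t).
- 31.5/40.5: SE 1.128, 3.1/1.128 = 2.75, power 78%.

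With the rounded d=0.67 and the normal approximation, the two cases give 75.8% and 80.5%.

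**4. Craving interaction, illustration only.** The document gives no craving effect or SD. Borrow the women's stress effect (2.4) and the stress SDs, and vary the men's effect:

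| Men's benefit | Interaction | Power, 31.5/31.5 | Power, 31.5/40.5 |
|---|---|---|---|
| None | 2.4 | 51% | 56% |
| Half the women's | 1.2 | 17% | 18% |

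With a smaller effect in women (0.5 SD), the same rows give about 29-32% and 11-12% (normal approximation).

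**5. Sensitivity to a smaller SD.** If repeated ratings and the pre-cue covariate cut the SD by 30% (an assumption), the SEs become 0.836 and 0.789. Power is then about 81-86% with no benefit in men and about 30-33% with half.

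**6. Overall progesterone versus placebo.** Detectable d at 80% power is 2.80 × sqrt(2/n): 0.50 with 63 per arm (31.5 + 31.5) and 0.47 with 72 per arm (31.5 + 40.5).

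**The case against.** - **A fuller calculation exists elsewhere.** C.2.d.3 refers to the Biostatistics Resource Core for the complete sample size estimation. This stands as a limit: one can say only that craving and withdrawal are not sized in this document. The general claim is nevertheless made here, and the basis shown here does not carry it.
- **The both-sexes citation is thin.** It concerns cue-induced cocaine craving and gives no effect sizes and no sex comparison. Section A.4 cites reduced cue-induced craving in cocaine-dependent women, and A.5 reports lower craving in women with high progesterone. C.1.e shows larger craving responses to stress in women than in men, although without testing progesterone. A reader might infer from the citation that the craving interaction is near zero. The documents do not support that, since a reduction in both sexes is compatible with a larger one in women. What stands is that the evidence is mixed.
- **An equal effect in both sexes is not a power failure.** The interaction test would then reject 5% of the time, but that is the type I error rate. The women-versus-men hypothesis would be false and a null interaction correct.
- **The overall contrast is already planned.** Aim 1 includes global treatment-group comparisons of cue response and withdrawal scores, listed as post hoc, and says interactions will be assessed. Aim 2 makes randomized treatment the primary independent variable and adds sex afterwards. So a reader should not infer that a shared craving benefit would go unexamined. The remaining risk is in how Hypothesis 2 is reported beside the power statement.
- **The craving figures borrow stress inputs.** True; they are illustrations. Step 5 shows that a smaller SD could bring the no-benefit case to 80% but leaves the half-benefit case far below it. The plan claims no such gain.

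**Conclusion.** The point holds as a mismatch between claim and basis. The 80% statement reaches craving and withdrawal, for which this document gives no progesterone effect size or SD. The stress interaction it does size includes an opposite-direction effect in men that cannot be assumed for craving. If the women's stress effect and SDs applied to craving, interaction power would be 51-56% with no benefit in men and 17-18% with half; these figures are conditional on those assumptions. For stress itself the design gives about 73-78% from the stated differences and SDs, or about 76-80.5% with d=0.67, depending on how many added men have usable data, so 80% or better is borderline at best. All of this assumes a two-sided test, 10% attrition and no precision gain from repeated measurement. The shortfall concerns the sex interaction; the overall treatment contrast has 80% power for d about 0.47-0.50.

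**What to change.** In the closing power statement of C.2.d.3:
- limit the interaction claim to the stress rating, and restate it as about 73-78% from the stated differences and SDs (or about 76-80.5% with d=0.67) after 10% attrition, saying how many added men are expected to have usable data;
- state that the craving and withdrawal interaction was not sized in this document, or quote the Biostatistics Resource Core calculation if there is one;
- give the detectable overall progesterone-versus-placebo difference, d about 0.47-0.50 at 80% power.

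In C.2.d.1, Aim 1, add one sentence to Hypothesis 2: report the already planned global treatment contrast alongside the treatment-by-sex interaction, each with a 95% CI, so that a null interaction is not read as no effect on craving.

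The cost is wording only, with no added participants, visits or data. The downside is a narrower and slightly lower stated power.

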1. RISKS TO THE SUBJECTS

a. Human Subjects Involvement and Characteristics

Admission into the study is open to men and women and to all racial and ethnic groups, age 18-45. 160 cannabis use disordered individuals (90 men and 70 women) will be recruited primarily through internet and newspaper advertisements. Inclusion/exclusion criteria that apply to all participants are listed below:

General Inclusion / Exclusion Criteria

Inclusion Criteria

1. Able to provide informed consent and function at an intellectual level sufficient to allow accurate completion of all assessment instruments.

2. Meet DSM-5 criteria for mild, moderate or severe cannabis use disorder (within the past three months) and report using cannabis at least five times weekly over the past month. While individuals may also meet criteria for mild use disorders of other substances, they must identify cannabis as their primary substance of abuse and must not meet criteria for any other moderate or severe substance use disorder (except tobacco) within the last 60 days.
3. Age 18-45.
4. For women, regular menses (every 25-35 days).
5. Consent to remain abstinent from alcohol for 12 hours prior to study visits, and all other drugs other than cannabis or nicotine for the duration of the study.
6. Women of childbearing potential must agree to utilize an effective means of birth control.
7. Must consent to random assignment.

Exclusion Criteria

1. Women who are pregnant, nursing or of childbearing potential and not practicing an effective means of birth control.
2. Women who are amenorrheic or using progesterone-based contraceptives.
3. Evidence or history of major medical illnesses, including liver diseases, abnormal vaginal bleeding, suspected or known malignancy, thrombophlebitis, deep vein thrombosis, pulmonary embolus, clotting or bleeding disorders, heart disease, diabetes, history of stroke or other medical conditions that the investigator deems as contraindicated for the individual to be in the study.
4. Subjects taking antipsychotics (unless for indication other than psychosis), or regularly taking opiates or benzodiazepines.
5. History of or current psychotic disorder or bipolar affective disorder.
6. Current suicidal or homicidal ideation/risk.
7. Known allergy to progesterone or peanuts (vehicle for micronized progesterone).
8. Unwilling or unable to maintain abstinence from alcohol 12 hours prior to study visits and all other drugs other than cannabis or nicotine for the duration of the study.
9. Meet DSM-5 criteria for moderate or severe substance use disorder (other than nicotine or cannabis) within the past 60 days.
10. Unable to comply with study procedures or pose threat to study staff.

b. Sources of Materials

Research material obtained from individual participants includes questionnaires and interviews with study personnel, ambulatory assessment data, and saliva and urine samples. To ensure confidentiality, all participant data will be letter/number coded, and only the investigators will have access to the master lists of codes. The research material will be obtained specifically for research purposes. Written research material obtained will be stored in the Addiction Sciences Division, in an office that is locked when not in use. Urine samples will be stored and processed in the Clinical Neurobiology Laboratory; saliva samples will be stored and processed in the Medical University of South Carolina Research Nexus Laboratory.

c. Potential Risks

1. Risks due to progesterone: Micronized progesterone is generally well tolerated. The most common adverse effect is headache. Other adverse effects that occurred at rates of 10% or more and at greater rates than placebo include headache, dizziness, abdominal cramps, breast pain, breast tenderness, joint pain, depression, dizziness, abdominal bloating, hot flashes, urinary problems, and vaginal discharge.
2. Risks due to study procedures: Participants will be asked not to smoke cannabis for 7 days. During this cannabis abstinence period, participants may experience symptoms of cannabis withdrawal such as craving cannabis, mild anxiety, insomnia, irritability, restlessness, stomachache, headache, nausea, loss of energy or appetite, chills, and diaphoresis. These symptoms are generally transient.
3. Potential risks of rating scales and questionnaires: These are all non-invasive, should add no risk, and have been used without difficulty or any adverse events in our previous studies. The only minor inconvenience could be the time taken to complete them. Some participants may feel uncomfortable disclosing personal thoughts and feelings.
4. Risks of stress induction procedures: There is a small risk of increased stress or cannabis craving as a result of the TSST and CREMA procedures; however, it will likely not differ substantially from the reactivity elicited by stimuli commonly encountered in the day-to-day environment of study participants. Participants that report sustained significant stress or craving after the laboratory session will be provided a debriefing to address symptoms.
5. Risks of blood draw: The risks of drawing blood include temporary discomfort from the needle stick, bruising, and infection. Fainting could occur.
6. Risks of loss of confidentiality: Careful efforts aimed at maintaining confidentiality have been effective in previous research, and only participants' code numbers will be recorded on the forms themselves to protect confidentiality. Phones provided by study staff to participants will be password protected to limit access to study assessments and pictures; participants utilizing their own phones will be asked to password protect their device for the duration of the study.

